Methods: Randomized single-blind single-centre controlled clinical trial with a 2x2 cross-over design. A sample of 42 patients attending to the outpatient gastroenterology unit at Clínica Fundadores in Bogotá city, who meet the inclusion criteria and have no exclusion criteria will be selected to participate. Included patients will be randomized to raise the head of bed with standard 20 cm-height wooden blocks or to sleep without bed inclination during the first 6 week period. After a 2 week washout period, allocation will be crossed and participants will be followed again during a second 6 week period. During the trial, every patient will receive standard pharmacological treatment with a proton pump inhibitor and/or sodium alginate and the researchers in charge of statistical analysis and reporting results will be blinded for the non pharmacological intervention under study. Primary outcome is a significant symptom reduction according to RDQ validated questionnaire and secondary outcomes include quality of life impact according to SF-36 validated questionnaire, patient preference and adverse events of non pharmacological intervention. Statistical analysis will be carried out with STATA 13.0 (Special Edition) statistical package for Windows. Differences with a p<0,05 will be accepted as statistically significant.

Expected results: Effectiveness of head of bed elevation in the treatment of patients with symptomatic nocturnal gastroesophageal reflux disease will be assessed. New knowledge for generation of a local and international recommendation about non pharmacological treatment of gastroesophageal reflux disease will be provided. Colombian researchers will be trained in methodological aspects concerning design, conduction and analysis of clinical trials in this field of medical knowledge.

Keywords: Gastroesophageal reflux disease, head of bed elevation, lifestyle measures, nocturnal symptoms, quality of life.

PROBLEM STATEMENT

Gastroesophageal reflux disease (GERD) is a clinical condition characterized by troublesome symptoms and medical complications as a result of reflux of gastric contents into the esophagus¹. GERD is diagnosed in 4% of primary care outpatient visits² and the disease prevalence in Latin-America reaches 12-31%³. Nocturnal symptoms have been found in 74% of patients with GERD and are a cause of significant quality of life impairment, when compared with general population and

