Cross-over: After allocation has been completed, patients in the intervention group will receive a pair of numbered wooden prisms with dimensions 20x18x18 cm along with written instructions about the correct use of the intervention. The patient must sleep with HBE during 6 weeks and both RDQ and SF-36 questionnaires will be applied again at the end of this first period while the participant is still sleeping with HBE. Afterwards, a washout 2 week period follows in which the participant sleeping with HBE will stop using it and will return the pair of wooden prisms to the researchers. After washout period has ended and both RDQ and SF-36 questionnaires have been applied again, patients allocated to the control group during the first period of the study will receive a random pair of prisms and will be instructed to use the prisms for sleeping with HBE during a second period of 6 weeks. Meanwhile, participants initially allocated to the HBE group will be followed as a control group in this second period of the study.

Blinding: Because HBE is not susceptible to double-blinding, patients allocated to the intervention group will always be aware of the group they belong to. However, the researcher in charge of statistical analysis of data and writing the results report will work with random-generated alphabetical group codes for masking the intervention in each one of the periods of the trial.

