Follow-up: After participant allocation, telephonic follow up will be made during both periods of the trial with a frequency that is dependent on the intervention group of the patient in that period. Participants in the HBE group will be called weekly for 2 weeks, and then will be called biweekly for a month, until each period of 6 weeks has ended. In contrast, patients in the control group will be called every three weeks along each period. With the purpose of verifying both HBE adherence and correct use of wooden prisms, every participant will be asked to send a photograph of the bed head legs during the follow-up telephone call. The photograph will be received by the researcher via e-mail or smartphone and will be encoded and saved in a hard disk. At the end of the first period, RDQ and SF-36 questionnaires will be applied and researchers will store the returned prisms during washout period. When washout period has ended, RDQ and SF-36 questionnaires will be applied again in order to be sure of the absence of any carry-over effect in the group initially allocated to HBE. Finally at week 14, RDQ, SF-36 and Patient Preference questionnaires will be administered to complete study ending outcome assessments.

In figure 5, a schematic representation of follow-up is shown.

[figure not shown]

Figure 5: Schematic representation of photographic and telephonic follow-up. W1-6: Weeks from 1st to 6th in each period.

Primary outcome:

1. Effectiveness: Change of ≥ 0,6 points between basal RDQ questionnaire and the same questionnaire administered after 6 weeks of HBE use.

Secondary outcomes:

- 1. Quality of life: Change of ≥ 10 percentage points between basal SF-36 questionnaire and the same questionnaire administered after 6 weeks of HBE use.
- **2. Patient preference:** Proportion of patients who preferred HBE, after finishing 14 weeks of the study.
- 3. Safety: Proportion of patients with any reported adverse event during HBE or without bed inclination.

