Statistic analysis plan: Quantitative and qualitative variables collected with Basic Data Format, RDQ, SF-36 and Patient Preference questionnaires will be typed in a Microsoft Excel 2007 database. Intervention groups will be masked with an alphabetical code provided by an independent collaborator who will not be involved with data analysis or report writing. For statistical processing, database will be imported into STATA SE 13.0 for Windows (StataCorp LP, Texas, USA) and descriptive statistics will be generated for each variable. Statistically significant differences will be searched for categorical data using the Chi-square test or Fisher exact test and normality will be tested for numerical continuous variables using the Shapiro-Wilk test. For normally distributed continuous variables, statistically significant differences will be searched for by using unpaired Student's t test. Alternatively, for not normally distributed variables Mann-Whitney U test will be applied. For non-normal variables due to atypical data, values outside the percentile 50 ± 1,5 interquartile range were excluded. For complementary processing of primary outcome and secondary outcome quality of life, score difference

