between periods will be transformed into a binomial variable and a McNemar marginal homogeneity test will be applied. McNemar mid-p was used if discordant pairs sum was smaller than 25²⁸. Differences with one-tail p<0,05 will be accepted as statistically significant. Exploratory subgroup analysis will search for differences stratified according to age group, sex, ethnic group, BMI, comorbidities, cups of coffee per day, pharmacological adherence, and length and severity of symptoms; among other 16 baseline variables. Subgroup interactions will be tested with Chi-square or Fisher exact test, and effect size was expressed as a univariate relative risk from a generalized linear model of binomial family. As part of internal quality control of the clinical trial, a pre-test was applied to prove the assumption of a negligible *carry-over* effect, according to expert guidelines²⁹. Analysis of variance (ANOVA) for crossover studies was used in search for significant sequence, period and treatment effects, assuming a negligible *carry-over* effect. In the modified intention to treat analysis, participants with protocol violations because of bad adherence to HBE, were included, but it was not possible to include patients who withdrew from the study because outcome information could not be gathered completely.

Methodology diagram: A schematic representation of the trial methodology is presented in figure 6.

[figure not shown]

Figure 6: Schematic representation of the trial methodology. RDQ: Reflux Disease Questionnaire; SF-36: Short Form 36 Questionnaire; HBE: Head of Bed Elevation; Standard treatment: Based on proton pump inhibitors and/or sodium alginate, according to treating physician criteria.

WORK TEAM

Work team of this clinical trial is formed by three authors. The respective roles during the design and conduction of the trial, and also the professional profiles of each researcher are described below.

Researchers:

- [name] (Principal Researcher study design, patient recruiting, telephonic follow-up, outcome assessment, statistical analysis, writing of final report)
 - General Practice Physician Universidad Nacional de Colombia
 - 3rd year Internal Medicine resident Universidad Nacional de Colombia
- [name](Researcher patient recruiting, intervention administration, clinical and telephonic follow-up, writing of final report)
 - General Practice Physician Universidad Nacional de Colombia

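### The masking of analyst and report writer cannot be relied on as described, because the researchers listed for those tasks also follow patients in a way that reveals allocation

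*Combined protocol and SAP*

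**What the plan says.** The title and the General design section call the trial single-blind. The Executive Summary (Methods) and General design both state what this means: "the researchers in charge of statistical analysis and reporting results will be blinded for the non pharmacological intervention under study". The Blinding section accepts that patients using head of bed elevation (HBE) know their group. It offers one safeguard: "the researcher in charge of statistical analysis of data and writing the results report will work with random-generated alphabetical group codes". The Statistic analysis plan adds that the groups are "masked with an alphabetical code provided by an independent collaborator who will not be involved with data analysis or report writing". No section says that the interviewer or the outcome assessor is masked.

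The Work Team section opens with "Work team of this clinical trial is formed by three authors". The principal researcher's duties, after study design, are "patient recruiting, telephonic follow-up, outcome assessment, statistical analysis, writing of final report". The second researcher's are "patient recruiting, intervention administration, clinical and telephonic follow-up, writing of final report". The third author's duties are not in the text available for this review, which is not a fault of the plan.

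The Follow-up section sets a call schedule that depends on the patient's group in the current period. It begins "Participants in the HBE group will be called weekly for 2 weeks" and then continues at a lower frequency, while controls are called every three weeks. At the call, each participant is asked for a photograph showing the legs at the head of the bed.

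**The concern.** Masking of analyst and report writer is all that stands behind the single-blind label. The role list gives both tasks to a researcher who also recruits, telephones and assesses the same patients. It gives report writing to a second researcher who administers the intervention. A letter in place of a group name does not remove what these people already know.

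This matters because the analysis plan leaves some decisions until the data are seen, and a masked analyst is the usual protection for such decisions. A reader who trusts the label would credit the result with a protection that the stated roles do not deliver.

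**Working it through.** No figure in the plan is in dispute, so the check sets the sections side by side.

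1. **Who is claimed to be masked.** Those who analyse and those who report (Executive Summary, General design, Blinding). Nobody else.

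2. **Who does that work.** Analysis: the principal researcher. Report writing: the principal and the second researcher (Work Team). Both also make follow-up calls.

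3. **What a caller learns.** For each 6-week period, from the Follow-up section:
   - HBE: weekly for 2 weeks = 2 calls. Then biweekly for a month, taken as 4 weeks. Read as every two weeks, 4 / 2 = 2 calls, so 2 + 2 = 4 in total. Read as twice a week, 4 × 2 = 8 calls, so 2 + 8 = 10 in total.
   - Control: 6 / 3 = 2 calls.

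   These counts are a reading of the text, because the figure showing the schedule is not available. Under either reading the arms differ (4 or 10 against 2). The schedule cannot be followed without knowing the patient's group, and the photograph shows whether the blocks are in place.

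4. **Whether the letter code protects against this.** The researcher "will work with random-generated alphabetical group codes for masking the intervention in each one of the periods of the trial". With two groups, there are two letters in a period. If the analyst recognises one patient whose allocation is known, that patient's letter is identified and the other letter follows. In a 2x2 cross-over the patient's condition in one period fixes the condition in the other, and a paired analysis must link the two periods, so the code for both is open. Knowing every patient is not required.

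5. **Whether recognition is plausible.** No section says that identifiers are removed before analysis, or that the analyst is kept away from follow-up records. The listed subgroup variables include age group, sex, BMI, comorbidities and coffee intake. In a trial of 42 patients, such a profile could point to a familiar patient.

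6. **What is left to judgement.** The Statistic analysis plan chooses the test after a Shapiro-Wilk test. It excludes outlying values where non-normality is attributed to them. It lists many subgroup variables and refers to 16 more without naming them. Several steps are in the past tense, so the text does not show that they were fixed before data were seen. By contrast, the responder cut-offs are fixed under the outcomes: 0.6 points on the RDQ and 10 points on the SF-36.

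**The case against.** The best defence is that a real coding step exists. The letters come from a person outside analysis and reporting, and the database is built from the basic data form, the questionnaires and the preference form. Call logs and photographs are not listed. This stands as far as it goes: nothing shows that allocation can be read from the file itself. It does not answer what the analyst knows already.

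A reader might infer that the masking is void, or that the analyst knows all 42 allocations in both periods. The documents do not support either. The coding step cannot be ignored. Two researchers share telephone follow-up, and the division of calls, photographs and assessments is not stated. The third author's duties cannot be seen, so a further analyst is possible, though that would not cancel the analysis role listed for the principal researcher.

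A reader might also infer that the primary result has been steered. No route to that is shown. The test choice follows a stated pre-test, the exclusion limit is numeric, the cut-offs are set and the subgroups are called exploratory. What remains open is mainly when non-normality counts as caused by outlying values, and which subgroups are reported.

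Three matters are separate. The plan never claims a masked outcome assessor, so listing outcome assessment among the duties does not itself contradict it. It does not say whether the questionnaires are self-completed. Allocation concealment at enrolment is not undermined by anything here.

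**Conclusion.** The point holds in limited form. The role list contradicts the masking statements, and the masking of analyst and report writer cannot be relied on as described. It extends beyond the analyst, because the second researcher administers the intervention and also writes the report.

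The conclusion rests on two assumptions: that the researchers carry out the duties listed for them, and that the codes label groups rather than individual patients, as the Blinding section indicates. At least the patients whom these researchers follow are known to them; the number cannot be determined. Nor can the size or direction of any bias be calculated.

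A properly masked analyst would still leave the RDQ and SF-36 reported by patients who know their group. The flaw is a design claim that should be corrected. It does not by itself invalidate the trial.

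**What to change.** Before the coded database is released:

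- Write, date and lock the analysis script with the independent collaborator. It should cover the choice of test, the rule for excluding outlying values (including when it applies) and the full subgroup list.
- Remove patient identifiers from the analysis file. This lowers the chance of recognition but does not remove it, since baseline characteristics remain.
- State in the protocol and the report which researchers had patient contact and also analysed or reported.

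If a team member without participant contact exists, assign the analysis to that person. Either that person also writes the results report, or the claim of masked reporting is dropped.

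If there is no such person, replace the single-blind label and the masked-analyst statements with 'open-label with coded data'. Locking the script limits discretion but does not restore masking. If the data have already been analysed, disclosure and relabelling remain possible.

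The cost is a short document and some rewording. The 42 patients, the visits, alpha and power are unchanged. The downside is a less favourable design label.

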Researchers declare no conflicts of interest. If such conflicts emerged during study conduction, they will be presented to the Medicine Faculty Ethics Committee at Universidad Nacional de Colombia. Likewise, this clinical trial is in accordance with article 13 from Ministerio de Salud Resolution 8430 of 1993, which highlights research institution responsibility of providing medical care to participants who suffer damage directly related to being part of a clinical trial.

TIMELINE OF ACTIVITIES

STAGE/ACTIVITY	Stage I (2 months)	S	tage	II (4 mc	onth	s)	Stage I	II (1 month)	Stage I	V (1 month)
			Adn	ninis	trati	ve						
Protocol writing	X											
Faculty Ethics Committee	X	X										
Wooden prism carving		X										
		:	Data	col	lecti	on						
Patient sampling			X	X								
Basal questionnaires			X	X	X	X	X	X				
Post-intervention questionnaires					X	X	X	X	X	X		
Database consolidation			X	X	X	X	X	X	X	X		
			Dat	ta an	alys	is						
Statistical analysis									X	X		
Literature review									X	X		
Results discussion										X		
		R	esul	ts di	sclo	sure						
Preliminary report									X		X	
Final report												X
Public dissertation												X
Original paper writing											X	X
Submit to publication												X

Table 2: Research Project proposed timeline

References

- [1] Vakil N, van Zanten SV, Kahrilas P, Dent J, Jones R. The Montreal definition and classification of gastroesophageal reflux disease: a global evidence-based consensus. *Am J Gastroenterol.* 2006; **101** (8): 1900-20; quiz 43.
- [3] Salis G. Revisión sistemática: epidemiología de la enfermedad por reflujo gastroesofágico en Latinoamérica. *Acta Gastroenterol Latinoam*. 2011; **41** (1): 60-9.
